- Investigator and his/her immediate family, defined as the investigator's spouse, parent, child, grandparent, or grandchild.

Source of Subjects

We plan to enroll up to 54 adults in order to achieve the goal of exposing up to 27 subjects. We plan to recruit participants from the referral pool of existing and new patients attending a specialty clinic for ASD at the Massachusetts General Hospital.

The Alan and Lorraine Bressler Clinical and Research Program for Autism Spectrum Disorder is a specialized ambulatory care program devoted to the assessment and treatment of individuals of all ages with ASD. It is one of only a few programs in the New England area to offer comprehensive assessment for individuals with ASD, including a complete psychiatric evaluation, psychopharmacological, neuropsychological, behavioral, and social services consultation, psycho-educational support and cognitive/behavioral therapies. The ambulatory care team consists of board-certified psychiatrists specialized in the assessment and management of ASD. Adults with ASD, the majority of whom are individuals with intact intellectual capacity and language skills, make up approximately one-third of the ASD population attending the clinic.

If a potential subject's clinician ascertains that the patient has an interest in study participation, the clinician will offer contact information for the study coordinator to the patient. The patient can then contact the study coordinator for more information on the trial. All subjects that enter the study will undergo standard screening and diagnostic procedures. Clinical records are not scanned in order to recruit subjects. Patients who potentially meet criteria for the study will only be contacted by their treating clinician and referred should the patient decide they wish to participate. If a patient of an investigator decides to enroll in the trial, the process of informed consent will be conducted with a co-investigator who does not treat the patient in a clinical setting. Under no circumstances will a physician investigator obtain informed consent from his or her own patient.

Subjects who have completed a previous clinical trial in our program may be eligible to participate in this study, as described in the Subject Enrollment section. Other medical records on a subject will not be used at any point during this study.

5. Subject Enrollment

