6. STUDY PROCEDURES

After providing written informed consent, all subjects will complete a clinical diagnostic interview via a virtual visit with a board-certified study clinician to assess eligibility. A study clinician will complete the Reproductive Potential Form. All subjects will be administered an assessment battery including a brief demographic interview and the SRS-2 (Pre-Screening). If an additional family member of the subject is available, we will ask that family member to independently complete an SRS-2 form. Both forms will be scored and the form with the higher score will be used to determine subject eligibility in order to reduce the possibility of under-recognition of social impairment.

We anticipate that subjects may enter this study following completion of/withdrawal from other ASD protocols in our office, and that there may be procedural overlap. So as to not burden subjects/parents/guardians with redundant time commitments, we will use the following diagnostic data previously collected: If a subject has completed an evaluation with one of the study clinicians and/or the structured diagnostic assessment in the three years prior to entrance into this study, he/she will not be asked to repeat any overlapping diagnostic procedures. We will use the study diagnostic data that had been previously collected so as to not burden the subject with redundant time commitments.

However, the study clinician will review the interval time period to assess for clinically significant medical or psychiatric history, to ensure that the subject meets appropriate study entrance criteria.

All female subjects of childbearing potential will have a urine pregnancy test that will be mailed to their address prior to Screening visit. If a participant has a positive urine pregnancy test, she will not be able to take part in the study. The study doctor will inform the participant of any positive test results.

Upon completion of Informed Consent, subjects will be randomized to receive either tPBM or sham and the respective device will be mailed. This study will include up to 27 subjects randomized at 1:1 ratio into 2 groups: tPBM and Sham.

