Primary outcome measure of efficacy will be reduction in ASD symptoms as measured by change from baseline on the clinician-rated SRS-2. Responders will be defined as those who demonstrate a $\geq 25\%$ reduction in SRS-2 total score *and* a score of 2 or 1 on the CGI-ASD-Improvement subscale ("much" or "very much improved").

Secondary outcome measure:

1. Treatment-related changes in associated psychopathology, social cognition, executive functions will be assessed by:
 - MGH Social-Emotional Competence Scale (MGH-SEC Scale; clinician- & observer-rated)

- Social Responsiveness Scale-Second Edition (SRS-2; self- & observer-rated)
- Adult Behavior Checklist (ABCL; self- & observer-rated)
- Behavior Rating Inventory of Executive Function-Adult Self Report Version (BRIEF-A) or parent version (BRIEF-P) for youth
- Adult ADHD Self-Report Scale (ASRS) & clinician-rated Adult ADHD Investigator Symptom Report Scale (AISRS) and CGI-ADHD scale
- Quality of Life Enjoyment and Satisfaction Questionnaire (Q-LES-Q)
- Hamilton Anxiety scale (HAM-A) & clinician-rated CGI-Anxiety scale
- Hamilton Depression scale (HAM-D) & clinician-rated CGI-Depression scale

2. Safety and tolerability will be assessed by:

- The monitoring of spontaneous treatment-emergent adverse events with the Clinician-rated Treatment-emergent Adverse Events Log (CTAE)
- tPBM Self-Report Questionnaire (TSRQ)

SAFETY

Consistent with good clinical practice, safety will be monitored at each study visit by a subject's assigned clinician. This clinician will be available 24 hours a day by page. The principal investigator will supervise all study activities including ratings and reported adverse events. All procedures have been designed to minimize subject discomfort, and no subject will be asked to engage in research procedures not outlined in the consent form.

If study participation is discontinued due to safety reasons, participants will receive three follow-up visits, giving adequate time for appropriate psychiatric care to be arranged.

Study Treatment

Safety will be monitored through treatment-emergent adverse events and subject rated TSRQ responses. Subjects will be monitored for adverse events at each visit. All adverse events will be recorded. A subject may be dropped from the study or dosage may be decreased at any time due to adverse events. All adverse events will be reported to the PHRC according to PHRC guidelines. All concomitant medications will be assessed at every study visit.

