54 subjects will be randomized (1:1) into the tPBM or placebo/sham group and be treated for 8 weeks post randomization. This design largely protects against the bias introduced by confounding factors.

We will rely on comparisons of the participants' performances in each study arm (placebo/sham and tPBM) at baseline prior to the initiation of treatment relative to their scores at the last assessment (completion/drop-visit). Since we are following subjects over a short period, missing data are not expected to impact our analyses such that standard statistical analyses will be employed. Specifically, we will employ longitudinal mixed-effects regression models (RM) with random effects for the subjects using Stata 16.0 (StataCorp, 2019). The RMs will use robust standard errors to account for the repeated measures on each subject. We will test binary data using mixed-effects logistic RMs, count data with mixed-effects Poisson RMs, and normally distributed data with mixed-effects linear RMs. Each model will predict outcome scores from treatment group (placebo/sham or tPBM), study visit (continuous predictor), and the treatment group-by-study visit interaction. All analyses will be intent to treat (ITT).

10. Monitoring and Quality Assurance

Consistent with good clinical practice, safety will be monitored at each study visit by a subject's assigned clinician. This clinician will be available 24 hours a day by page. The principal investigator will supervise all study activities including ratings and reported adverse events. All procedures have been designed to minimize subject discomfort, and no subject will be asked to engage in research procedures not outlined in the consent form.

Safety will be monitored through treatment-emergent adverse events. Subjects will be monitored for adverse events at each visit. All adverse events will be recorded. A subject may be dropped from the study or dosage may be decreased at any time due to adverse events. All adverse events will be reported to the PHRC according to PHRC guidelines. All concomitant medications will be assessed at every study visit.

All adverse events will be recorded from the time of Informed Consent through study completion, or termination. The Adverse Event CRF must be completed and submitted to the IRB and Niraxx, as required. Regulations for adverse event handling and reporting contained in the FDA and ICH Guidelines will be adhered to.

Overview and Definitions

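### The blanket intent-to-treat sentence in Section 9 is not limited to efficacy and no safety analysis set is defined, so subjects randomised but never exposed could be counted in adverse-event rates

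*Combined protocol and SAP*

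**What the plan says.** Section 9 (Statistical Analysis) describes mixed-effects models by arm and visit: "Each model will predict outcome scores from treatment group (placebo/sham or tPBM), study visit (continuous predictor". It gives models by data type without naming endpoints: "We will test binary data using mixed-effects logistic RMs, count data with mixed-effects Poisson RMs". It ends with "All analyses will be intent to treat (ITT". Neither safety nor any adverse-event rate is mentioned there.

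Safety is part of Primary Aim 1 in Section 2. Under DATA ANALYSIS it is item 2 of the secondary outcomes: "Safety and tolerability will be assessed by" two instruments, the adverse-event log and the tPBM Self-Report Questionnaire (TSRQ). The log entry reads "The monitoring of spontaneous treatment-emergent adverse events with the Clinician-rated Treatment-emergent Adverse Events Log (CTAE". No analysis method or population is attached to either.

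On timing, Section 6 says "Upon completion of Informed Consent, subjects will be randomized to receive either tPBM or sham and the respective device will be mailed". Treatment starts only after the Week 0 visit (Devices and Dosing), where the application sites are inspected for lesions that would rule out treatment.

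On numbers, Section 4 (Source of Subjects) says "We plan to enroll up to 54 adults in order to achieve the goal of exposing up to 27 subjects". Section 6 randomises at most 27. Section 9 randomises 54.

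**The concern.** Intent-to-treat is the usual choice for comparing efficacy because it preserves the randomised comparison. For safety, the usual question is what happened to people who used the device. A subject who never used it cannot have a device-related event, so including that subject makes the treatment look better tolerated and shrinks the absolute difference between arms. For safety, that errs in the wrong direction.

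The design makes such subjects plausible. Read literally, randomisation follows consent directly. It therefore comes before completion of eligibility screening, any washout and the baseline skin check. Section 5 accepts that some people who consent will not qualify, and ineligibility is a listed reason for removal (Withdrawal from the Study). With arms this small, one or two subjects visibly move a percentage.

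**Working it through.** The plan contains no adverse-event rate, sample-size calculation or safety denominator, so there is no figure to reproduce. The check is a sensitivity calculation.

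**Inputs**
- Arm size: 27 randomised 1:1 (Section 6) gives arms of 13 and 14.
- Unexposed share u: not stated. I take zero, one or two non-starters in an arm of 14.
- Events among exposed subjects: not stated. I use 3 subjects with an event, for illustration only.

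**Formula.** Let x exposed subjects have an event, with n_e exposed and n_r randomised. If non-starters contribute no events:

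rate over randomised = x / n_r = (x / n_e) × (n_e / n_r) = exposed rate × (1 - u)

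**Results, arm of 14**

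| Non-starters | Factor (1 - u) | Exposed rate | Rate over all randomised |
|---|---|---|---|
| 0 | 14/14 = 1.00 | 3/14 = 21.4% | 3/14 = 21.4% |
| 1 | 13/14 = 0.93 | 3/13 = 23.1% | 3/14 = 21.4% |
| 2 | 12/14 = 0.86 | 3/12 = 25.0% | 3/14 = 21.4% |

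If u is the same in both arms, the absolute difference is multiplied by (1 - u) and the rate ratio does not change.

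**Direction.** Section 10 records adverse events from consent onwards. Suppose the single non-starter has an event before any session and it is counted. The rate over randomised is then (3 + 1)/14 = 28.6%, above the exposed rate of 23.1%. Dilution therefore depends on pre-exposure events being left out of the count.

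**The one safety proportion in the protocol.** Section 10 (Data Safety Monitoring Board) stops the study if more than 40% of active-arm patients have had a serious adverse event. It does not say whether this means randomised or exposed patients. The smallest count exceeding 40% is floor(0.4n) + 1:
- n = 14: 0.4 × 14 = 5.6, so 6.
- n = 13: 0.4 × 13 = 5.2, so 6.
- n = 12: 0.4 × 12 = 4.8, so 5.

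One non-starter leaves the trigger unchanged; two move it by one subject.

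**The case against.** The strongest reply is that Section 9 never names safety. Its intent-to-treat sentence closes a paragraph about scores, and adverse-event handling begins in Section 10. On that reading no safety denominator has been specified, so none is diluted. This is fair: applying the sentence to safety is a literal reading, not a stated safety rule. It does not remove the problem, because on the narrower reading the plan has no safety population at all and needs the same correction.

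Other wording points towards exposed subjects. Section 10 defines an adverse event in terms of a subject who uses a device, the outcome is treatment-emergent events, and Table II first schedules the TSRQ at Week 1. These passages limit what enters the numerator. They do not say who is in the denominator, so they do not answer the point.

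A reader might infer that rates would be halved, for example from 3/13 = 23.1% to 3/27 = 11.1%, by taking 54 randomised and 27 exposed. The documents do not support this. Section 9 says its 54 are both randomised and treated. Section 6 caps randomisation at 27, which matches the 27 exposed in Section 4. Section 5 counts anyone who signs consent as enrolled, so 54 enrolled and 27 exposed reads naturally as screening loss. Halving takes one number from each of two conflicting statements.

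A reader might also infer that the plan favours a safe conclusion by construction. That is too strong: events are recorded from consent, so non-starters can add events, and equal non-starting leaves the rate ratio unchanged. Nor does anything in the documents suggest that wrong-device shipments are expected. Grouping by device received is a standard precaution, not a response to a known fault.

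**Conclusion.** The point holds in a limited form. The intent-to-treat sentence has no efficacy limit, no safety set exists, and randomisation before mailing makes never-exposed subjects a realistic possibility. Counting them multiplies event rates by (1 - u), on the assumption that they contribute no counted events. The size runs from none, if all start, to a factor of 0.93 or 0.86 for one or two non-starters in an arm of 14. The number of non-starters is my assumption, because the documents do not state it. No larger effect can be claimed until Sections 4, 6 and 9 agree on how many subjects are randomised. This is worth correcting because safety is in the primary aim and the correction is small.

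**What to change.** In Section 9:
- Limit the intent-to-treat sentence to efficacy analyses.
- Define a safety set of all subjects who started at least one session, grouped by the device actually received, and summarise treatment-emergent adverse events and the TSRQ in it.
- List events between consent and the first session separately.

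In Section 10, state whether the denominator of the 40% serious-adverse-event proportion is randomised or exposed subjects. Reconcile the number randomised across Sections 4, 6 and 9.

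The cost is a few sentences. Reported event rates may look slightly less favourable. The first-session date is not guaranteed from device data: under Subject Confidentiality, the manufacturer supplies adherence data only for subjects who consent to that access. For the others it must come from the compliance review recorded in REDCap at each visit. The accountability logs, as described, list equipment, receiving date and serial number but not which subject had which device, so a link from serial number to subject and device type should be kept under the existing blinding arrangements.

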APPENDIX A

Data Monitoring Committee / Data and Safety Monitoring Board Appendix

- *To be completed for studies monitored by Data Monitoring Committee (DMC) or Data and Safety Monitoring Board (DSMB) if a full DMC/DSMB charter is not available at the time of initial IRB review.*
- *DMC/DSMB Charter and/or Roster can be submitted to the IRB later via Amendment, though these are not required.*

A Data Monitoring Committee (DMC) or Data and Safety Monitoring Board (DSMB) will be convened for safety monitoring of this research study. The following characteristics describe the DMC/DSMB convened for this study (Check all that apply):

- The DMC/DSMB is independent from the study team and study sponsor.
- A process has been implemented to ensure absence of conflicts of interest by DMC/DSMB members.
- The DMC/DSMB has the authority to intervene on study progress in the event of safety concerns, e.g., to suspend or terminate a study if new safety concerns have been identified or need to be investigated.
- Describe number and types of (i.e., qualifications of) members:
[name]
[name]
[name]
- Describe planned frequency of meetings:
Once every six months.
- DMC/DSMB reports with no findings (i.e., “continue without modifications”) will be submitted to the IRB at the time of Continuing Review.
- DMC/DSMB reports with findings/modifications required will be submitted promptly (within 5 business days/7 calendar days of becoming aware) to the IRB as an Other Event.

Appendix B

Table II. Study Schema

Weeks	99	0	1	2	3	4	6	8
Visits	Screen	Baseline	W1	W2	W3	MP	W6	EP/ ET
Informed Consent	X							
tPBM Test Dose								
tPBM Device Subject Training		X						
tPBM Initial Titration:			X					
Day 1-3, 20 min/day								
Day 4-7, 30 min/ day								
tPBM Treatment - 40 min/day			X					
tPBM Treatment - 50 min/day				X	X	X	X	X
Diagnostic Assessments								
Inclusion/Exclusion Criteria	X							
Psychiatric Evaluation & Medical History	X							
Physiological Procedures								
Virtual Examination of Exposure Sites		X	X	X	X	X	X	X
Urine pregnancy test	X*	X*	X*	X*	X*	X*	X*	
Clinician-Rated Assessments								
Pregnancy Potential/Monitoring Form	X	X		X		X	X	
MGH-SECS-C	X					X		X
AISRS		X				X		X
HAM-A		X				X		X
HAM-D		X				X		X
CGIs	X	X	X	X	X	X	X	X
CTAE		X	X	X	X	X	X	X
Concomitant Medications	X	X	X	X	X	X	X	X
GAF	X	X	X	X	X	X	X	X
Progress Note		X	X	X	X	X	X	X
Subject-Rated Assessments								
Demographic Interview	X							
SRS-2	X					X		X
ASRS		X				X		X
BRIEF-A		X				X		X
Q-LES-Q		X				X		X
TSRQ			X	X	X	X	X	X
Observer-Rated Assessments								
SRS-2	X							X
MGH-SECS-I	X							X
ABCL	X							X

Appendix C

Table III. Flexible Titration Schedule

Day	Maximum Total Dose (minutes)
1-3	20
4-7	30
8	40
15	50
